4. PATIENT SELECTION

The study population will consist of multiple myeloma patients requiring therapy who have relapsed and/or are refractory to their last therapy and have been treated with at least 1, but not more than 5, lines of multiple myeloma therapy. Prior therapy must have consisted of at least 1 regimen that included lenalidomide and/or bortezomib. Patients should be considered to be appropriate candidates for a clinical study by their treating physicians.

- Relapsed patients must have previously achieved \geq MR on at least 1 line of therapy as assessed by the treating physicians.
- Refractory patients are allowed, but it is not required that patients be refractory to their last therapy.
- Primary refractory patients are allowed in the Phase 1b portion of the study only.

The following definitions will be used to classify multiple myeloma disease state:

- Refractory multiple myeloma: Disease that is nonresponsive while on primary or salvage therapy or progresses within 60 days of last therapy. Nonresponsive disease is defined as either failure to achieve minimal response (MR) or development of progressive disease (PD) while on therapy.
- Relapsed and refractory myeloma: Disease that is nonresponsive while on salvage therapy, or progresses within 60 days of last therapy in patients who have achieved MR or better at some point previously before progressing in their disease course.
- Primary refractory myeloma: Disease that is nonresponsive in patients who have never achieved an MR or better with any therapy. It includes patients who never achieve MR or better in whom there is no significant change in M-protein and no evidence of clinical progression, as well as primary refractory PD where patients meet criteria for true PD.
- Relapsed multiple myeloma: Previously treated myeloma that progresses and requires the initiation of salvage therapy but does not meet the criteria for either “primary refractory myeloma” or “relapsed-and-refractory myeloma.”

4.1 INCLUSION CRITERIA

1. Diagnosis of multiple myeloma with measurable disease as indicated by 1 or more of the following:
 - a. Serum M-protein \geq 500 mg/dL
 - b. Urine M-protein \geq 200 mg/24 hour
 - c. Only for subjects without measurable serum and urine M-protein, serum free light chain: Involved free light chain (FLC) level \geq 10 mg/dL, provided serum FLC ratio is abnormal
2. Patients requiring therapy who have relapsed and/or are refractory to their last therapy and have been treated with at least 1, but not more than 5, lines of multiple myeloma

- therapy. Prior therapy must consist of at least 1 regimen that included lenalidomide and/or bortezomib. Patients should be considered to be appropriate candidates for a clinical study by their treating physicians. Relapsed patients must have previously achieved \geq MR on at least 1 line of therapy as assessed by the treating physician. Refractory patients are allowed, but it is not required that patients be refractory to their last therapy. Primary refractory patients are allowed in the Phase 1b portion of the study only.
3. Males and females \geq 18 years of age
 4. Eastern Cooperative Oncology Group Performance Status (ECOG PS) 0–2
 5. Adequate hepatic function, with bilirubin \leq 1.5 times the upper limit of normal (ULN) in the absence of Gilbert’s disease or hemolysis, aspartate aminotransferase (AST) \leq 3 times ULN, and alanine aminotransferase (ALT) \leq 3 times ULN
 6. Absolute neutrophil count (ANC) \geq 1000 cells/mcL, hemoglobin \geq 7.0 g/dL, and platelet count \geq 30,000 cells/mcL:
 - a. Patients must not have received platelet transfusions for at least 1 week prior to Screening.
 - b. Screening ANC must be independent of granulocyte colony-stimulating factor (G-CSF) and granulocyte-macrophage colony-stimulating factor (GM-CSF) support for at least 1 week and of pegylated G-CSF for \geq 2 weeks prior to first dose.
 - c. Patients may receive red blood cell (RBC) transfusions or receive supportive care with erythropoietin or darbepoetin in accordance with institutional guidelines.
 7. Calculated or measured creatinine clearance (CrCl) rate of \geq 30 mL/min calculated using the formula of Cockcroft and Gault $[(140 - \text{age}) \times \text{mass (kg)} / (72 \times \text{serum creatinine mg/dL})]$. Multiply result by 0.85 if female.
 8. Uric acid, if elevated, must be corrected to within laboratory normal range before dosing
 9. Patients must sign written informed consent form (ICF) in accordance with federal, local, and institutional guidelines
 10. Female patients of childbearing potential must have a negative serum or urine pregnancy test within 3 days prior to receiving the first dose and agree to use effective methods of contraception during the study and for 3 months following the last dose of study drug. Postmenopausal females ($>$ 45 years old and without menses for $>$ 1 year) and surgically sterilized females are exempt from these requirements. Male patients must use an effective barrier method of contraception during the study and for 3 months following the last dose if sexually active with a female of childbearing potential.

11. Prior carfilzomib is not required but is allowed if a patient had at least 2 cycles of carfilzomib alone or in combination with a dose of at least 20/27 mg/m², as long as the patient:
 - a. Had at least a partial response to prior carfilzomib therapy
 - b. Was not removed from carfilzomib therapy due to toxicity, unless approved by the medical monitor
 - c. Was not removed from carfilzomib therapy for progressive disease nor experienced progressive disease within 6 months after any prior carfilzomib therapy.

4.2 EXCLUSION CRITERIA

1. Radiation therapy within 2 weeks prior to first dose; localized radiation therapy within 1 week prior to first dose
2. Immunotherapy/standard myeloma therapy within 2 weeks prior to first dose (except for antibody therapy, where 6 weeks is required, and alkylator therapy, where 3 weeks is required); prior stem cell transplant (SCT) therapy (autologous SCT within the prior 8 weeks; allogeneic SCT within the prior 16 weeks). Patients with prior allogeneic SCT should not have evidence of moderate to severe graft-versus-host disease (GvHD), as defined in [Filipovich \(2005\)](#)
3. Plasmapheresis is not permitted at any time during the Screening period or while the subject is receiving study treatment. If a subject has started screening procedures requiring plasmapheresis, or is anticipated to require plasmapheresis during or after the Screening period, this patient will be considered ineligible and should not be enrolled.
4. Glucocorticoid therapy within 14 days prior to enrollment that exceeds a cumulative dose of 160 mg of dexamethasone or equivalent
5. Participation in an investigational therapeutic study within 3 weeks prior to first dose
6. Prior oprozomib exposure
7. Known hypersensitivity/toxicity or intolerance to dexamethasone
8. Major surgery within 3 weeks prior to first dose
9. Congestive heart failure ([CHF] New York Heart Association Class III to IV), symptomatic ischemia, conduction abnormalities uncontrolled by conventional intervention, or myocardial infarction within 6 months prior to first dose
10. Uncontrolled hypertension or uncontrolled diabetes
11. Active infection requiring systemic antibiotics, antivirals, or antifungals within 2 weeks prior to first dose
12. Known or suspected human immunodeficiency virus (HIV) infection or patients who are HIV seropositive

13. Active hepatitis A, B, or C infection
14. History of previous clinically significant GI bleed in the last 6 months prior to first dose
15. Significant neuropathy (Grade 3, Grade 4, or Grade 2 with pain) at the time of the first dose
16. Other malignancy within the past 3 years with the exception of adequately treated basal cell carcinoma of the skin, squamous cell skin cancer, thyroid cancer, carcinoma in situ of the cervix, carcinoma in situ of the breast, prostate cancer of Gleason Score 6 or less with stable prostate specific antigen levels, or cancer considered cured by surgical resection
17. Plasma cell leukemia
18. Female patients who are pregnant or nursing
19. Inability to swallow medication, inability or unwillingness to comply with the drug administration requirements, or GI condition that could interfere with the oral absorption or tolerance of treatment
20. Any contraindication to oral hydration (e.g., significant preexisting comorbidity or fluid restriction)
21. Any clinically significant psychiatric or medical condition that, in the opinion of the investigator, could increase patient risk or interfere with protocol adherence or a patient's ability to give informed consent

5. SUBJECT ENROLLMENT

The Screening period for a particular subject commences after the subject signs the ICF. The ICF must be signed before any study-specific tests may be performed. Every subject who signs an ICF will be assigned a study number.

After a subject has been screened and has successfully fulfilled all eligibility criteria, the site representative will submit the completed Inclusion/Exclusion Checklist to **the Sponsor**. Please see the Study Reference Manual for contact information.

Each subject will be assigned a study- and site-specific sequential number by the site staff. This number will be used to identify each subject throughout the clinical study and will be used on all study documentation related to that subject.

Documentation must include start and stop dates for prior treatment. Disease progression must be documented with appropriate disease assessment parameters. Copies of all Screening

laboratory results are required.

Subjects who initially fail Screening but subsequently become eligible may still be enrolled in the study.

Sites that do not enroll a single subject within the first 6 months of initiating the study may be terminated at the discretion of the sponsor.

6. TREATMENT PROCEDURES

6.1 DRUG ADMINISTRATION

Oprozomib Tablets will be supplied containing 60, 90, or 120 mg of oprozomib. Oprozomib ER Tablets will be supplied containing 150, 180, 210, 240, or 270 mg of oprozomib. Both types of tablets will be administered in single daily doses ([Table 3](#), [Table 4](#), and [Table 5](#)). Refer to the Pharmacy Manual for handling, administration, and storage instructions.

Oprozomib will be administered orally, once daily, on either the 5 consecutive day bimonthly schedule or the 2 consecutive day weekly schedule for each 14-day treatment cycle ([Figure 1](#)), either at the single-dose level (i.e., continuous dosing) or step-up dose level, and the treatments will be repeated until disease progression, unacceptable toxicity, or study treatment discontinuation for any reason (see [Section 8](#)). Oprozomib will be administered in combination with dexamethasone at 20 mg orally (or intravenously, if tablets are unavailable or subject cannot tolerate tablets) on Days 1, 2, 8, and 9 for both treatment schedules. On oprozomib dosing days (i.e., on Days 1 and 2 for both schedules and Days 8 and 9 for the 2 consecutive day weekly schedule), dexamethasone must be taken at least 30 minutes prior to oprozomib. On days in which PK sampling is taken after a dose, oprozomib must be taken in the fasted state (at least 2 hours after a meal and fasting for at least 2 hours after dosing). On all other days, including non-PK days and days in which only a predose PK sample is taken, it is recommended that oprozomib is administered with food (i.e., within approximately 30 minutes after eating).

Subjects may be premedicated pro re nata (as needed [PRN]) with a 5-hydroxytryptamine type-3 (5-HT₃) inhibitor, such as ondansetron or granisetron, before administration of the first dose of oprozomib each day and around the clock. Procedures for dose reductions and adjustments are summarized in [Section 6.4](#).

In the Phase 1b portion, subjects will be dosed in treatment cohorts in escalating order (see [Section 3.1.2: Table 3, Table 4, and Table 5](#) for doses/cohorts, and see [Section 6.2](#) for methods of dose escalation to the MTD), as determined by the CSRC and sponsor, only after the safety of the previous dose level has been established or until an MTD has been determined.

In the Phase 2 portion, subjects will be dosed at the recommended Phase 2 dose, as defined in the Phase 1b portion of the study (see [Section 3.1.2: Table 3, Table 4, and Table 5](#) for doses/cohorts, and see [Section 6.2](#) for methods of dose escalation to the MTD).

6.1.1 SWITCHING TO OPROZOMIB ER TABLETS FROM OPROZOMIB TABLETS

When subjects on Oprozomib Tablets switch to the Oprozomib ER Tablets, additional PK assessment will be obtained before and after changing formulations ([Section 7.4.1](#)).

6.2 PHASE 1B

6.2.1 SAFETY CONSIDERATIONS FOR PHASE 1B

Treatment cohorts will be dosed in escalating order (see [Section 3.1.2: Table 3, Table 4, and Table 5](#)) as determined by the CSRC and sponsor, only after the safety of the previous dose level has been established or until an MTD has been determined; de-escalation may be performed after the MTD is exceeded and for individual subjects based on tolerability.

Subsequent cohorts may initiate treatment at the starting dose (of 150 mg for 5/14 or 240 mg for 2/7) but will not be dosed at the step-up dose to be studied until safety data are obtained from at least 3 evaluable subjects in the previous cohort at the step-up dose for Cycle 2. Rules for dose escalation are presented in [Section 6.2.2](#). Safety will be evaluated based on the incidence, relatedness, and severity of AEs, clinical laboratory test results, electrocardiograms (ECGs), and other relevant clinical findings as provided by the investigators. A review of safety data for each cohort will be conducted by the CSRC and sponsor when all of the above data are available.

The CSRC, which comprises **the Sponsor's** medical monitor, **the Sponsor's** drug safety representative, and the investigators, will review all clinical and laboratory data and must agree whether dose escalation to the next cohort is appropriate. As PK data from each treatment cohort become available, they may also be reviewed by the CSRC. All available clinical data

will be considered for dose-escalation decisions.

6.2.2 DOSE-ESCALATION RULES

The planned and contingent dose levels are provided in Section 3.1.2 (Table 3, Table 4, and Table 5), and dose escalation rules are provided in Table 6. Additional details can be found in the Cohort Management Plan.

Table 6: Dose-Escalation Rules

No. of Evaluable Subjects with Treatment-related DLT at a Given Dose Level	Dose Escalation Rules
0 of 3	Next cohort of 3 subjects treated at the next planned higher dose level.
1 of 3	Up to 3 more subjects are treated at that same dose level.
≥ 2 of 3	Dose escalation stops. Three more subjects will be added to the next lower dose level, unless 6 subjects have already been treated at that dose level.
1 of 6	Next cohort of 3 subjects treated at the next planned higher dose level.
≥ 2 of 6	Dose escalation stops. Additional subjects may be treated at the next lower dose level, for a minimum of 6 subjects treated at that dose level.
Highest dose with < 2 of 6	Maximum tolerated dose

Source: Modified from Simon 1997.

DLT = Dose-limiting toxicity.

Intrasubject dose escalation to the recommended Phase 2 dose may be permitted once that dose has been determined and after discussion between the treating physician and the **Sponsor** medical monitor.

6.3 DOSE-LIMITING TOXICITY

Subjects will be evaluated for DLT according to the NCI-CTCAE (Version 4.03). Subjects with SD or better may continue treatment.

During the Phase 1b portion, assessment of DLTs will occur during the first 14 days of treatment with continuous dosing (Cycle 1) or during the first 14 days of treatment with the step-up dose to be studied during the 2-week assessment period (Cycle 2). Any subject who develops a DLT during the assessment period after receiving at least 1 dose of oprozomib in the

assessment period will be considered evaluable. Any subject who does not develop a DLT, but has not received all planned doses of oprozomib and dexamethasone, will be considered unevaluable and will be replaced.

Guidelines for withholding study treatment, including treatment delays, reintroduction, and discontinuation, are described in [Section 6.4.1](#). “Study drug-related” is defined as a reasonable likelihood of clinical causality based on time of event, biology, and dechallenge improvement, and that the AE was not likely explained by the subject’s clinical state, underlying disease, concomitant medication, or study/nonstudy procedure. For the purposes of this study, a DLT is defined as any of the following treatment-related events occurring in the first 14 days of treatment, with treatment at the dose to be studied (i.e., Cycle 1 for continuous dosing or Cycle 2 for step-up dosing):

Any \geq Grade 3 nonhematologic AE, with the following exceptions or qualifications:

- \geq Grade 4 abnormalities in serum creatinine or electrolytes will be considered a DLT.
- \geq Grade 3 acute kidney injury, defined as serum creatinine $> 3 \times$ baseline or > 4.0 mg/dL of any duration will be considered a DLT.
- Grade 3 nausea, vomiting, diarrhea, or constipation will be considered a DLT only if lasting for > 7 days despite optimal supportive care, including (at a minimum) a 5-HT₃ antagonist and aprepitant or fosaprepitant for nausea and vomiting, and loperamide (e.g., Imodium), and diphenoxylate/atropine (e.g., Lomotil) for diarrhea.
- Grade 3 fatigue lasting > 14 days will be considered a DLT.
- Asymptomatic Grade 3 hypophosphatemia lasting less than 24 hours will not be considered a DLT.
- \geq Grade 3 dexamethasone-related toxicities will not be considered DLTs.

Any of the following hematologic AEs will be considered a DLT:

- Grade 4 neutropenia: ANC < 500 cells/mcL lasting ≥ 7 days
- Febrile neutropenia: Any single temperature $\geq 38.3^\circ\text{C}$ or a sustained temperature of $\geq 38.0^\circ\text{C}$ for over 1 hour with \geq Grade 3 neutropenia (ANC < 1000 cells/mcL)
- Grade 3/4 thrombocytopenia
 - Grade 3 thrombocytopenia of any duration with Grade 2 bleeding or requiring platelet transfusion
 - Grade 4 lasting ≥ 7 days

- Grade 4 lasting < 7 days with Grade 2 bleeding, or if platelet counts are lower than 10,000 cells/mcL, requiring a platelet transfusion

Note: The following will not be considered a DLT:

- Grade 4 anemia
- Grade 4 thrombocytopenia lasting < 7 days with platelet counts above 10,000 cells/mcL without clinically significant bleeding and with or without transfusion

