10.1 STUDY ENDPOINTS

Primary Endpoints

Phase 1b

- Dose-limiting toxicities identified to determine the MTD and RP2D, defined as the highest dose at which < 33% of subjects experience DLTs after 1 cycle (14 days Cycle 1 for continuous dosing and Cycle 2 for step-up dosing) of treatment.
- Safety and tolerability

Phase 2

- Overall response status, to determine whether a subject has a best response of sCR, CR, VGPR, or PR, as defined by IMWG-URC, and MR or nCR per EBMT criteria ([Appendix H](#))
- Safety and tolerability

Secondary Endpoints

Phase 1b/2

- Pharmacokinetics of Oprozomib Tablets and Oprozomib ER Tablets

Phase 2

- Clinical benefit response status, to determine whether a subject has a best response of sCR, CR, VGPR, or PR, as defined by IMWG-URC, and MR or nCR per EBMT criteria ([Appendix H](#))
- Duration of response, defined as the time from first evidence of PR or better to confirmation of disease progression or death due to any cause
- Progression-free survival, defined as the time from the start of treatment to disease

- progression or death due to any cause
- Time to progression, defined as the time from first dose to disease progression
 - Time to response, defined as time from the start of study treatment until the start of the first confirmed response (PR or better).

Exploratory Endpoints

Phase 1b/2

- Pharmacodynamics and proteomic biomarkers
- Genomic biomarkers that may potentially predict for response and resistance following treatment with proteasome inhibitors

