8.2 Interim Analysis and Data Monitoring

The CSRC will review the clinical data of each dose cohort after three subjects have been treated for at least one cycle during phase 1 of the study. Based on the number of subjects with dose-limiting toxicity, escalation to the next higher OPZ dose may occur, the cohort may be expanded to six subjects, or dosing at that dose level may stop and the

next-lower dose cohort may be expanded. The committee must agree that dose escalation to the next cohort is appropriate before it proceeds.

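### The 14-day DLT window conflicts with the duration-based DLT criteria, and the plan does not say how an event still unresolved at Day 14 is counted

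*Protocol*

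**What the plan says.** **The window.** Protocol 6.3 states that "a DLT is defined as any of the following treatment-related events occurring in the first 14 days of treatment", at the dose under study. The synopsis and 3.1.1 place the assessment in the same 14 days. The endpoint in 10.1 is the dose at which fewer than 33% of subjects "experience DLTs after 1 cycle (14 days Cycle 1 for continuous dosing and Cycle 2 for step-up dosing) of treatment".

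**The duration criteria.** Four criteria in 6.3, repeated in the synopsis, need a minimum duration:
- Fatigue: "Grade 3 fatigue lasting > 14 days will be considered a DLT".
- Gastrointestinal (GI): "Grade 3 nausea, vomiting, diarrhea, or constipation will be considered a DLT only if lasting for > 7 days".
- Neutrophils: "Grade 4 neutropenia: ANC < 500 cells/mcL lasting ≥ 7 days".
- Platelets: "Grade 4 lasting ≥ 7 days".

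**The decision.** Table 6 in Protocol 6.2.2 escalates on the number of evaluable subjects with a DLT. SAP 2.1 opens the next dose level when none of the first three subjects has had a DLT in Cycle 1. SAP 8.2 has the Cohort Safety Review Committee (CSRC) review the data "after three subjects have been treated for at least one cycle during phase 1 of the study". The DLT listing in SAP 7.6.1 is confined to the first cycle. Protocol 6.2.1 has the CSRC meet once the cohort's safety data are in, lets it weigh everything on hand, and requires its agreement. Further escalation details are left to a Cohort Management Plan (3.1.2, 6.2.2), which is not among the documents.

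**The concern.** A criterion that needs more days than the window holds cannot be applied as written. A criterion that needs half the window can be applied only to events that start in the first half. Neither document says whether *occurring* refers to the onset of the event or to the day its duration is reached, and neither says how an event still running at Day 14 enters the count.

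The count decides escalation and the maximum tolerated dose (MTD). If a pending event is entered as no DLT, the 3+3 rule works on a rate below the true one and passes the dose more often than it should.

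The event types concerned are relevant to this drug. In Study 2011-001 the DLTs at the highest 2/7 dose were Grade 3 diarrhea and Grade 4 thrombocytopenia (Protocol 1.4.2). The one 2/7 DLT reported so far in this study was Grade 4 thrombocytopenia (1.4.3).

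**Working it through.** The plan states no figure on this point, so there is none to reproduce.

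**Step 1: which onsets can be complete by Day 14.** Let d be the minimum duration in calendar days, counted inclusively. More than 14 days gives d = 15, more than 7 gives d = 8, and 7 or more gives d = 7. The latest onset complete by the end of Day 14 is 14 − d + 1. An event starting on Day 14 is complete on Day 14 + d − 1.

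| Criterion | d | Latest onset complete by Day 14 | Complete on, if onset is Day 14 |
|---|---|---|---|
| Grade 3 fatigue | 15 | none (14 − 15 + 1 = 0) | Day 28 |
| Grade 3 GI event | 8 | Day 7 | Day 21 |
| Grade 4 neutropenia | 7 | Day 8 | Day 20 |
| Grade 4 thrombocytopenia | 7 | Day 8 | Day 20 |

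If elapsed days are counted instead, the limits are one day earlier: Day 6 for GI events and Day 7 for the cytopenias.

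**Step 2: the schedules.** On 5/14 all oprozomib doses fall on Days 1 to 5. On 2/7 two of the four fall on Days 8 and 9 (Protocol 3.1). No duration-defined event that starts on Day 9 or later can be complete by Day 14. A subject whose event starts after the Day 9 dose may have taken every planned dose. Under 3.1.1 that subject is evaluable, and at Day 14 has no completed DLT.

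**Step 3: what an undercount would do.** The share of DLTs that would be missed is not in the documents, so it is an assumption, f, shown from 10% to 50%. The true rate p is set at 33%, the threshold in the protocol's MTD definition. A cohort passes with 0 of 3 DLTs, or with 1 of 3 and then 0 of 3:

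P(pass) = q³ + 3pq² · q³, with q = 1 − p.

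At p = 0.33 this is 0.67³ + 3 × 0.33 × 0.67⁵ = 0.301 + 0.134 = 0.434. If a share f is missed, p is replaced by p(1 − f). Cohorts 501, 502 and 601 are planned with six subjects at once. For them the chance of fewer than 2 DLTs in 6 is q⁶ + 6pq⁵.

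| f (assumed) | Rate seen | P(pass), 3+3 | P(fewer than 2 of 6) |
|---|---|---|---|
| 0 | 0.330 | 0.434 | 0.358 |
| 10% | 0.297 | 0.500 | 0.427 |
| 25% | 0.2475 | 0.605 | 0.540 |
| 50% | 0.165 | 0.783 | 0.741 |

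These figures take subjects as independent and suppose that a missed event is never reclassified.

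**The case against.** Several points on the other side have force.

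- **Onset reading.** *Occurring* may mean onset in the window. That is the reading that gives the fatigue criterion any content, and under it an event completed later still counts. This stands as a possible reading, but the documents do not state it, and it does not settle what is counted if review comes first.
- **CSRC discretion.** Protocol 6.2.1 escalates only once the previous level's safety is established, and a committee that includes the investigators would see a Grade 3 or 4 event in progress. One cycle in SAP 8.2 is a minimum, not a fixed decision day. All this permits waiting. It does not say how the event is classified, while Table 6 counts DLTs and SAP 2.1 is worded as a direct rule.
- **Follow-up exists.** Protocol 9.3.1 already follows drug-related adverse events to resolution or stabilization, so the outcome would be known in time. What is missing is the link to the DLT count.
- **Cohort Management Plan.** It may cover the point. It was not available, so this cannot be ruled out. A rule that defines the MTD should still be visible in the protocol and SAP.
- **Late stage.** Amendment 4 follows completion of the study's analysis (Protocol 1), so little escalation is left to affect. The definition still determines how the reported DLT counts are read.

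**Conclusion.** The conflict is real. Read literally, the fatigue criterion can never be met in the 14-day window. The GI and cytopenia criteria may be undetermined at Day 14 when onset is after about Day 7 or 8, including events that follow the Day 8 and 9 doses on 2/7. Followed as written, SAP 2.1, 7.6.1 and 8.2 allow a pending event to be counted as no DLT.

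Three stronger conclusions might be inferred, and the documents do not support them:
- *That several criteria can never be met.* Only fatigue is impossible. The other three can be met with early onset, and a prolonged Grade 4 thrombocytopenia was counted as a DLT on 5/14 (Protocol 1.5.1).
- *That second-week doses on 2/7 cannot produce a DLT.* Febrile neutropenia, acute kidney injury and Grade 3 thrombocytopenia with Grade 2 bleeding or transfusion, among others, need no 7- or 14-day wait.
- *That DLTs are in fact being missed and the MTD is biased upward, most on 2/7.* No data on pending events are given. The rise from 0.43 to between 0.50 and 0.78 shows how sensitive the rule is to an assumed missed share. It does not estimate a bias.

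**What to change.** Keep every clinical threshold. Reconcile the DLT text in the synopsis, Protocol 3.1.1, 6.2.1, 6.3 and 10.1, and SAP 2.1, 3.1, 7.6.1 and 8.2, so that:

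1. DLT status is defined by onset in the 14-day window, with the duration outcome ascertained after Day 14 where the criterion needs it.
2. The DLT count used under Table 6 states how an event still unresolved at the time of review is classified.
3. The SAP listing includes events with onset in the window whose duration criterion is met later.

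How escalation timing is aligned with this is for the sponsor and the CSRC to decide. If the Cohort Management Plan already has a rule, it should be carried into these sections.

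The change is one of wording. Its cost is an occasional delay before a subject's DLT status is final. With onset on Day 14, that is until Day 20 for cytopenias, Day 21 for GI events and Day 28 for fatigue.
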